**- Frequency of THU and Dec ingestion:**

Oral THU ~10 mg/kg is administered 60 minutes before oral decitabine ~0.2 mg/kg 2X/week on consecutive days if there is no  $\geq$  grade 3 treatment-related non-hematologic toxicity and the ANC is  $>0.5 \times 10^9/L$  (if ANC is  $<0.5 \times 10^9/L$ , treatment is held until recovery above this threshold then resumed with a dose reduction as per Table 1).

- Patients will be required to have the treatment on the same consecutive days every week. If patients miss a dose they need they can make up the dose the same week ( $\pm 3$  days) and the study team needs to be notified.

- G-CSF neutropenia prophylaxis is recommended 1X/week if the ANC is  $<1.5 \times 10^9/L$

**If there is stable disease or partial response by RECIST v1.1 at the week 8 or 16 staging CTs, and there are no treatment-related  $\geq$  grade 3 toxicities, and blood count trends (trends in the absolute neutrophil, absolute lymphocyte and platelet counts) suggest that such treatment-related toxicities are not imminent, the dose of THU and Dec can be increased by one capsule each. THU-Dec dose increases should not occur**

more often than every 4 weeks and only to a maximum of 2 additional capsules of each drug from the starting dosage.

-Pre-medications are not required, since nausea, vomiting and diarrhea are not anticipated with this non-cytotoxic mode of therapy.

Dose modifications (dose reductions, dose escalations) of oral THU-Dec are described in Section 7.0

Reported adverse events and potential risks of oral THU-Dec are described in Section 8.0

No investigational or commercial agents or therapies other than those described below may be administered with the intent to treat the subject's malignancy.

### **6.3 General Concomitant Medications**

The following medications are prohibited during the study (unless utilized to treat a drug-related adverse event):

- a) Immunosuppressive agents
- b) Immunosuppressive doses of systemic corticosteroids
  - Any concurrent antineoplastic therapy (ie, chemotherapy, hormonal therapy, immunotherapy, extensive radiation therapy, or standard or investigational agents for treatment of NSCLC Palliative and supportive care for disease related symptoms may be offered to all subjects on the trial. Palliative (limited-field) radiation therapy is permitted for subjects who have investigator assessed clinical benefit. However, radiation to target lesions is not permitted. For example patients with asymptomatic oligo-metastatic brain metastatic disease that would clinically be amenable to Gamma Knife Radiosurgery is allowed on the protocol so long as they are not having systemic disease progression and per investigator are receiving clinical benefit from the trial.
  - Inter-current illness that prevents further administration of treatment
  - The investigator considers it, for safety reasons, to be in the best interest of the subject
  - Unacceptable treatment related toxicity, NCI CTC AE version 4.0 Grade 3 or 4 that fails to recover to baseline or < Grade 3 in the absence of treatment within 4 weeks See section 6.1.1, 6.1.2 and 6.1.3.
  - Subject decision to withdraw from treatment (partial consent) or from the study (full consent)
  - Pregnancy during the course of the study for a child-bearing participant
  - Death, or
  - Sponsor reserves the right to temporarily suspend or prematurely discontinue this study.
  - The date and reason for discontinuation must be documented. Every effort should be made to complete the appropriate assessments

### **6.5 Stopping Rule**

If 3 of the first 5 patients in the THU-Dec + nivolumab arm are removed from study for grade 3/4 non-hematologic toxicity or toxicities prior to cycle 2 that are likely attributable to THU-Dec, the study will be terminated.

The study incorporates a two-stage design in the experimental THU-Dec + nivolumab arm. If after the 1st stage of 20 patients in the THU-Dec+nivolumab arm, 2 or fewer respond, the trial will be stopped and the null hypothesis that THU-Dec+nivolumab is no better than nivolumab will be accepted, else the trial continues for an additional 20 patients.

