**Non-Hematologic Toxicity ≥ Grade 3:**

Hold drug until recovery to grade 1 or baseline then resume with a reduction in dose by 1 capsule each of Dec and THU. If recurrent toxicity occurs, interrupt drug administration and after recovery from the toxicity, resume therapy with a decrease in frequency of administration to 1X/week. The overall goal is to sustain regular administration at a lower dose if necessary, rather than infrequent administration of a higher dose. Only continue treatment if it is judged to be in the best interests of the patient.

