### **8.4 Reporting Procedures for Serious Adverse Events**

Since there is an early stopping rule for this clinical trial (Section 6.4), all AEs related to toxicity that cause patients to withdraw from the study in the first 5 patients should be reported to the DSTC in “real-time”.

For the purposes of safety reporting, all adverse events will be reported that occur on or after Cycle 1 Day 1, through 30 days after the final dose of study drug. Adverse events, both serious and non-serious, and deaths that occur during this period will be recorded in the source documents. All SAEs should be monitored until they are resolved or are clearly determined to be due to a subject’s stable or chronic condition or intercurrent illness(es). Related AEs will be followed until resolution to baseline or grade 1 or stabilization.

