#### **8.4.1 SAE Reporting Requirements**

Participating investigators (all sites) must report all serious adverse events to the Sponsor within **24 hours** of discovery or notification of the event. The participating investigator must also provide follow-up information on the SAE until final resolution. Sponsor contact:

- [name], [[contact]](mailto:[contact]) and research coordinator, [name], [[contact]](mailto:[contact])

The Sponsor will review the SAE and report the event to the FDA, external collaborator(s), and IRB as applicable.

It is the Sponsor-Investigator's responsibility (e.g. lead site PI) to ensure that ALL serious adverse events that occur on the study (e.g. ALL SAEs that occur at each enrolling institution) are reported to all participating sites.

All SAEs should simultaneously be faxed or e-mailed to BMS at:

Global Pharmacovigilance & Epidemiology  
Bristol-Myers Squibb Company  
[contact]  
Email: [[contact]](mailto:[contact])

- An SAE report should be completed for any event where doubt exists regarding its seriousness.
- For studies with long-term follow-up periods in which safety data are being reported, include the timing of SAE collection in the protocol.
- If the investigator believes that an SAE is not related to study drug, but is potentially related to the conditions of the study (such as withdrawal of previous therapy or a complication of a study procedure), the relationship should be specified in the narrative section of the SAE Report Form.
- If only limited information is initially available, follow-up reports are required. (Note: Follow-up SAE reports should include the same investigator term(s) initially reported.)
- If an ongoing SAE changes in its intensity or relationship to study drug or if new information becomes available, a follow-up SAE report should be sent within 24 hours to BMS using the same procedure used for transmitting the initial SAE report. All SAEs should be followed to resolution or stabilization. All SAEs should be followed to resolution or stabilization.

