### **Discontinuation Criteria**

Treatment should be permanently discontinued for the following:

- Any Grade 2 drug-related uveitis or eye pain or blurred vision that does not respond to topical therapy and does not improve to Grade 1 severity within the re-treatment period OR requires systemic treatment
- Any Grade 3 non-skin, drug-related adverse event lasting > 7 days, with the following exceptions for drug-related laboratory abnormalities, uveitis, pneumonitis, bronchospasm, hypersensitivity reactions, and infusion reactions, and endocrinopathies:
  - Grade 3 drug-related uveitis, pneumonitis, bronchospasm, hypersensitivity reaction, or infusion reaction of any duration requires discontinuation
  - Grade 3 drug-related endocrinopathies adequately controlled with only physiologic hormone replacement do not require discontinuation
  - Grade 3 drug-related laboratory abnormalities do not require treatment discontinuation except those noted below
    - Grade 3 drug-related thrombocytopenia > 7 days or associated with bleeding requires discontinuation
    - Any drug-related liver function test (LFT) abnormality that meets the following criteria require discontinuation:
      - AST or ALT > 8 x ULN
      - Total bilirubin > 5 x ULN
      - Concurrent AST or ALT > 3 x ULN and total bilirubin > 2 x ULN
- Any Grade 4 drug-related adverse event or laboratory abnormality, except for the following events which do not require discontinuation:
  - Isolated Grade 4 amylase or lipase abnormalities that are not associated with symptoms or clinical manifestations of pancreatitis and decrease to < Grade 4 within 1 week of onset.
  - Isolated Grade 4 electrolyte imbalances/abnormalities that are not associated with clinical sequelae and are corrected with supplementation/appropriate management within 72 hours of their onset

- Grade 4 lymphopenia or leucopenia
- Grade 4 drug-related endocrinopathy adverse events, such as adrenal insufficiency, ACTH deficiency, hyper- or hypothyroidism, or glucose intolerance, which resolve or are adequately controlled with physiologic hormone replacement (corticosteroids, thyroid hormones) or glucose-controlling agents, respectively, may not require discontinuation after discussion with and approval from the Investigator
- Any dosing interruption lasting > 6 weeks with the following exceptions:

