- a) Patients will receive Nivolumab every 2 weeks ( $\pm$  4 days per protocol) (4 weeks i.e 2 treatments=1 cycle) until progression (by RECIST v1.1) or unacceptable toxicity. A treatment break for upto 6 weeks for will be allowed upon discussion with study PI
- b) Patients will be monitored post study every 12 weeks ( $\pm$  3 weeks) for post-study treatment status, clinical safety updates and survival; these could be done by review of patient's medical records or contacting patient's medical provider or the subject.
- c) Patients disease will be monitored with CT scans of the chest, abdomen and pelvis after every 2 cycles (i.e prior to every odd cycle  $\pm$  7 days) or sooner if clinically indicated;
- d) Patients who have recent ( $<$ 6 weeks from start of study treatment) tissue biopsy or patients who have had recurrence after surgery within 6 months of surgical resection may be eligible without a fresh biopsy; Rest of the patients will require a biopsy prior to study enrollment. Patients will require a repeat biopsy in 6-10 weeks post treatment prior to cycle 3 of nivolumab. If the biopsy is felt to be high risk by the treating physician or interventional radiologist, an exception may be made upon discussing with the PI.
- e) For Cycle 1 Day 1 (C1D1) labs, screening labs can be used if  $\leq$ 1 week; pregnancy tests need to be done within 24hrs of first dose.

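### The early toxicity stop counts removals, so grade 3/4 events that are held and re-dosed under Section 7.1 neither count toward it nor, if non-serious, reach the DSTC promptly: a cheap improvement, not an error

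*Combined protocol and SAP*

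**What the plan says.** All sections cited are in the combined protocol and SAP.

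- **The stop.** Section 6.5 terminates the study if three of the first five patients in the THU-Dec plus nivolumab arm "are removed from study for grade 3/4 non-hematologic toxicity or toxicities prior to cycle 2 that are likely attributable to THU-Dec". This is the only numeric toxicity boundary. The other rule in 6.5 concerns response.
- **Managing the same event.** For non-hematologic toxicity of grade 3 or more, Section 7.1 says: "Hold drug until recovery to grade 1 or baseline then resume with a reduction in dose by 1 capsule each of Dec and THU". If it recurs, dosing resumes once weekly after recovery. Continuing is left to a judgement of the patient's best interests.
- **Reporting tied to the stop.** Section 8.4 cites the early stopping rule and says that "all AEs related to toxicity that cause patients to withdraw from the study in the first 5 patients should be reported to the DSTC", in real time.
- **Routes to removal.** The discontinuation reasons printed under Section 6.3 include subject decision, investigator judgement ("The investigator considers it, for safety reasons, to be in the best interest of the subject") and unacceptable toxicity of "Grade 3 or 4 that fails to recover to baseline or < Grade 3 in the absence of treatment within 4 weeks". Section 9.3 adds permanent discontinuation criteria, among them "Any Grade 3 non-skin, drug-related adverse event lasting > 7 days", with listed exceptions.
- **Cycle length.** Note a to the Section 10.0 calendar gives "4 weeks i.e 2 treatments=1 cycle".
- **Serious events.** Sections 8.4.1 and 8.6 send every SAE to the sponsor within 24 hours and to the DSTC at the same time. Section 8.7 defers to the cancer center's monitoring plan, which is not in the documents.

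**The concern.** A stop meant to detect early harm should depend mainly on how toxic the regimen is. This one also depends on what the site does after the event. Of two sites seeing identical grade 3/4 toxicity, the one that follows the Section 7.1 default adds nothing to the count, while the one that takes the patient off adds one. The real-time reporting in Section 8.4 has the same trigger, so it does not fill the gap.

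What is at stake is an early signal of frequent but recovering toxicity in the first patients given THU-Dec with nivolumab on this trial. The primary endpoint, the error rates and the sample size are not affected.

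**Working it through.** **The plan's own safety figure.** Section 3.2 gives the chance of seeing at least one event of 5% risk as 64% with 20 patients and 87% with 40. Both reproduce: 1 − 0.95^20 = 0.6415 and 1 − 0.95^40 = 0.8715. The plan gives no operating characteristics for the 3-of-5 rule.

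**Inputs.** From Section 6.5: five patients, boundary three. Two quantities are not in the documents and are assumed over a range:
- q, the true rate of grade 3/4 non-hematologic toxicity likely attributable to THU-Dec;
- r, the share of affected patients who are removed rather than held and resumed.

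**Formula.** With p = q × r and independent patients, P(stop) = P(Bin(5, p) ≥ 3) = 10p³(1 − p)² + 5p⁴(1 − p) + p⁵. Any removal that follows a qualifying event is counted, which is the reading most favourable to the rule.
- p = 0.10: 0.0081 + 0.00045 + 0.00001 = 0.0086
- p = 0.20: 0.0512 + 0.0064 + 0.0003 = 0.0579
- p = 0.40: 0.2304 + 0.0768 + 0.0102 = 0.3174

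| True rate q | Half removed | Three-quarters removed | All counted |
|---|---|---|---|
| 5% | 0.02% | 0.05% | 0.1% |
| 10% | 0.1% | 0.4% | 0.9% |
| 20% | 0.9% | 2.7% | 5.8% |
| 30% | 2.7% | 7.9% | 16.3% |
| 40% | 5.8% | 16.3% | 31.7% |

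The last column is also the chance that an onset-based count of three in five would be reached.

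**If exactly three of five are affected,** all three must be removed, so P(stop) = r³: 0.5³ = 12.5%, or 0.75³ = 42%.

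**Timing.** The cycle 2 limit in Section 6.5 could refer to onset or to removal, and to one or both limbs of the sentence. The choice matters for the non-recovery route. A cycle is 28 days and that route needs 4 weeks off treatment. An event starting on day d of cycle 1 could lead to removal by that route no earlier than day d + 28, which is day 29 or later. Under a removal reading it could not count unless the start of cycle 2 was delayed; under an onset reading it could.

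**The case against.** The strongest reply is that the plan contains no contradiction. Terminating for toxicity that patients cannot tolerate, while managing toxicity that recovers, is a coherent split, and the rule and its reporting trigger count the same thing. That stands.

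The gap is also narrow:
- Section 8.2.2 makes hospitalization, life-threatening events and important medical events SAEs, and Section 8.4.1 adds that "An SAE report should be completed for any event where doubt exists regarding its seriousness". A reader might infer that the DSTC is blind to early toxicity. The documents do not support that: all SAEs reach it at once. The reporting gap is limited to clearly non-serious events that are held and resumed.
- A reader might also infer that the stop cannot fire because Section 7.1 directs re-dosing. It can, through investigator judgement, subject decision, non-recovery or the Section 9.3 criteria. The last of these sit in the nivolumab section and concern stopping treatment, but they are a route to removal.
- The monitoring plan behind Section 8.7 may cover these events. One can say only that the protocol text does not.

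The expected rate is low. Section 8.1 reports no non-hematologic toxicity of grade 2 or more from decitabine in the earlier non-cytotoxic studies. Section 8.2 (Tetrahydrouridine) describes only blood-count effects for oral THU-Dec at these doses, and no significant non-hematologic events for a THU analog with decitabine at about 2 to 3 times the dose. None of this was with nivolumab, but it makes the 20% to 40% rows a case of unexpected toxicity.

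Finally, counting onsets does not make a sensitive rule. It stays silent 94% of the time at a 20% rate and 68% at 40%, because five patients with a boundary of three is the main limit. This stands too, and it is why the prompt report of each onset is worth more than the changed count.

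What the reply does not remove is that no numeric boundary applies to retained patients, even those with an SAE, and that the protocol text gives no prompt DSTC route for the non-serious events.

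**Conclusion.** The point holds as a cheap safety improvement, not as an error in the plan. As written, the chance of reaching the only numeric toxicity stop depends on whether sites remove or re-dose affected patients. At assumed rates of 20% and 40%, having half of them removed cuts it from 5.8% to 0.9% and from 32% to 5.8%. At 10% the difference is under one percentage point. These sizes rest on assumed values of q and r and on independent patients.

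The benefit is limited to the case where the combination is more toxic than earlier experience suggests. The unclear scope of the cycle 2 limit is a separate, smaller matter of wording, and it should be settled in the same edit.

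**What to change.** - **Section 8.4.** For the first five THU-Dec patients, report to the DSTC in real time each grade 3/4 non-hematologic toxicity likely attributable to THU-Dec with onset in cycle 1 (the first 28 days), whether or not the drug is resumed.
- **Section 6.5.** Hold accrual for DSTC review if three of the first five have such an onset. Keep termination if three of five are removed, and add termination if the DSTC so advises. State that the cycle 2 limit refers to onset.

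The cost is a few extra expedited reports and a small chance of an unnecessary pause: 0.1% at a true rate of 5%, 0.9% at 10% and 5.8% at 20%. The result would be a review, not termination. No patients are added. Attribution to THU-Dec remains investigator judgement, so some dependence on the site stays.

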### **6.6 Duration of Follow Up**

Subjects will be followed for toxicity for 30 days after treatment has been discontinued, until start of new anti-cancer treatment or until death, whichever occurs first. The clinical course of each event will be followed until resolution, stabilization, or until it has been determined that the study treatment or participation is not the cause, unless the event exceeds 6 months in duration. Serious adverse events that are still ongoing at the end of the study period will necessitate follow-up to determine the final outcome. Any serious adverse event that occurs after the study period and is considered to be possibly related to the study treatment or study participation will be recorded and reported immediately. All randomized subjects who discontinue study treatment must continue to be followed for collection of outcome and/or survival follow-up data every 2 months until death or subjects withdraw consent from all study related activities. The survival and toxicity follow up of the patients could be by telephone or through review of medical records.

### **6.7 Post Study Access to Therapy**

At the conclusion of the study, subjects who continue to demonstrate clinical benefit will be eligible to receive study drug. Study drug will be provided via an extension of the study, a rollover study requiring approval by responsible health authority and ethics committee, or through another mechanism at the discretion of the sponsor. The sponsor reserves the right to terminate access to study drug if any of the following occur: a) the marketing application is rejected by responsible health authority; b) the study is terminated due to safety concerns; c) the subject can obtain medication from a government sponsored or private health program; or d) therapeutic alternatives become available in the local market.

## **7.0 DOSE MODIFICATION**

Potential dose modifications of oral THU-Dec include dose reductions and dose escalations, described in sections below.

### **7.1 Dose Reduction of THU-Dec**

**Table 1** lists standard laboratory values that should trigger dose reduction of the investigational drug oral THU-Dec.

#### **Table 1: Trigger Values that Result in Dose Reduction of oral THU-Dec**

Measurement	Trigger value for Dose Modification	Dose Modification
Absolute neutrophil count (ANC)	<0.5 x 10  /L (non-cytotoxic DNMT1-depletion shifts normal hematopoietic differentiation away from neutrophils towards platelets and hemoglobin)	Hold treatment with THU-Dec until ANC ≥ 0.5 x 10  /L, then restart with decrease in dose by 1 capsule each of Dec and THU. If recurrent toxicity occurs, interrupt study drug administration until recovery from toxicity then resume with a reduction in treatment frequency of THU-Dec to 1X/week. If toxicity recurs at this dose, interrupt study drug until toxicity resolved then resume at same dose and frequency. The overall goal is to sustain regular administration, at a lower dose if necessary, rather than infrequent administration of a higher dose, however, a minimum dose is required to produce DNMT1 depletion. Only continue treatment if it is judged to be in the best interests of the patient. Only continue treatment if it is judged to be in the best interests of the patient. G-CSF growth factor support is recommended if ANC is <1.5 x 10^9/L.
Absolute lymphocyte count	<0.5 x 10  /L	Hold treatment with THU-Dec until absolute lymphocyte count ≥ 0.5 x 10  /L, then restart with decrease in dose by 1 capsule each of Dec and THU. If recurrent toxicity occurs, interrupt study drug administration until recovery from toxicity then resume with a reduction in treatment frequency of THU-Dec to 1X/week. If toxicity recurs at this dose, interrupt study drug until toxicity resolved then resume at same dose and frequency. The overall goal is to sustain regular administration, at a lower dose if necessary, rather than infrequent administration of a higher dose, however, a minimum dose is required to produce DNMT1 depletion. Only continue treatment if it is judged to be in the best interests of the patient.
Platelets	>1,200 x 10  /L (see above, differentiation shifts with non-cytotoxic DNMT1-depletion)	Withhold until platelets ≤ 1,200 x 10  /L, then restart with decrease in dose by 1 capsule each of Dec and THU. If recurrent toxicity occurs, interrupt study drug administration until recovery from toxicity then resume with a reduction in

	can increase platelet counts)	THU-Dec frequency to 1X/week. If toxicity recurs at this dose, interrupt study drug until toxicity resolved then resume at same dose and frequency. The overall goal is to sustain regular administration, at a lower dose if necessary, rather than infrequent administration of a higher dose, however, a minimum dose is required to produce DNMT1 depletion.
Hemoglobin	Hemoglobin >17g/dl (differentiation shifts with non-cytotoxic DNMT1-depletion can increase hemoglobin)	Withhold until hemoglobin ≤17 g/dl, then restart with decrease in dose by 1 capsule each of Dec and THU. If recurrent toxicity occurs, interrupt study drug administration until recovery from toxicity then resume with a reduction in THU-Dec frequency to 1X/week. If toxicity recurs at this dose, interrupt study drug until toxicity resolved then resume at same dose and frequency. The overall goal is to sustain regular administration, at a lower dose if necessary, rather than infrequent administration of a higher dose, however, a minimum dose is required to produce DNMT1 depletion.
Serum creatinine	
≥1.6 mg/dL (if pre-treatment value <0.5mg/dL)
 
≥1.7 mg/dL (if pre-treatment value 0.6-0.8 mg/dL)
 
Doubling of creatinine (if pre-treatment value 0.9-2.9 mg/dL)
	Neither Dec nor THU are known to be nephrotoxic. Consider other causes of worsening renal function. If no other causes are identified, hold THU-Dec until levels recover below threshold, then restart with decrease in dose by 1 capsule each of Dec and THU. If recurrent toxicity occurs, interrupt study drug administration until recovery from toxicity then resume with a reduction in THU-Dec frequency to 1X/week. If toxicity recurs at this dose, interrupt study drug until toxicity resolved then resume at same dose and frequency. The overall goal is to sustain regular administration, at a lower dose if necessary, rather than infrequent administration of a higher dose, however, a minimum dose is required to produce DNMT1 depletion.
ALT	ALT ≥ 2.5X the upper limit of normal	Neither Dec nor THU are anticipated to be hepatotoxic. Consider other causes of worsening liver function (e.g., hepatitis). If no other causes

		
are identified, hold THU-Dec until levels recover below threshold, then restart with decrease in dose by 1 capsule each of Dec and THU. If recurrent toxicity occurs, interrupt study drug administration until recovery from toxicity then resume with a reduction in THU-Dec frequency to 1X/week. If toxicity recurs at this dose, interrupt study drug until toxicity resolved then resume at same dose and frequency. The overall goal is to sustain regular administration, at a lower dose if necessary, rather than infrequent administration of a higher dose, however, a minimum dose is required to produce DNMT1 depletion.

--	--	--

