##### **Adequate Organ Function Laboratory Values**

System	Laboratory Value
---------------	-------------------------

Hematological	
Absolute neutrophil count (ANC)	$\geq 1,500$ /mcL
Platelets	$\geq 100,000$ / mcL
Hemoglobin	$\geq 8.5$ g/dL or $\geq 5.6$ mmol/L
Renal	
Serum creatinine OR Measured or calculated a creatinine clearance	$\leq 1.5$ X upper limit of normal (ULN) OR  $\geq 30$ mL/min for subject with creatinine levels > 1.5 X institutional ULN
Hepatic	
Serum total bilirubin	$\leq 1.5$ X ULN OR
	Direct bilirubin $\leq$ ULN for subjects with total bilirubin levels > 1.5 ULN
AST (SGOT) and ALT (SGPT)	$\leq 2.5$ X ULN OR $\leq 5$ X ULN for subjects with liver metastases
Albumin	$\geq 2$ mg/dL
a Creatinine clearance should be calculated per institutional standard.	

8. Patients with leptomenigeal disease are not eligible but patients with brain metastases are eligible – these patients should commence treatment on study > 1 week after completion of gamma knife or whole brain radiotherapy or >4 weeks after surgical resection of brain metastasis. Patients should ideally be off steroids at the start of study treatment, however patients on steroid taper and a dose of no more than 2mg/day of dexamethasone can begin study treatment; and steroids should be tapered off as quickly as clinically feasible. Repeat brain MRI after radiation is not required for eligibility but is strongly recommended, to establish the pre-treatment baseline status of any brain metastases, necessary to accurately assess for response or progression.

Patients with untreated, asymptomatic brain metastasis not requiring steroids are also eligible, however, these patients need to be discussed with the study PI prior to being registered.

9. Subjects must have the ability to understand and the willingness to sign a written informed consent document.

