**Nivolumab administration should be delayed for the following:**

Any Grade  $\geq 2$  non-skin, drug-related AE, with the following exceptions:

- Grade 2 drug-related fatigue or laboratory abnormalities do not require a treatment delay
- Any Grade 3 skin, drug-related AE
- Any Grade 3 drug-related laboratory abnormality, with the following exceptions for lymphopenia, leukopenia, AST, ALT, total bilirubin, or asymptomatic amylase or lipase:
  - Grade 3 lymphopenia or leukopenia does not require dose delay.
  - If a subject has a baseline AST, ALT, or total bilirubin that is within normal limits, delay dosing for drug-related Grade  $\geq 2$  toxicity.
  - If a subject has baseline AST, ALT, or total bilirubin within the Grade 1 toxicity range, delay dosing for drug-related Grade  $\geq 3$  toxicity.

Any AE, laboratory abnormality, or intercurrent illness which, in the judgment of the investigator, warrants delaying the dose of study medication.

**Subjects who require delay of nivolumab should be re-evaluated closely as clinically indicated and resume nivolumab dosing when re-treatment criteria are met.**

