**Criteria to Resume Treatment**

Subjects may resume treatment with study drug when the drug-related AE(s) resolve to Grade  $\leq 1$  or baseline value, with the following exceptions:

- Subjects may resume treatment in the presence of Grade 2 fatigue
- Subjects who have not experienced a Grade 3 drug-related skin AE may resume treatment in the presence of Grade 2 skin toxicity
- Subjects with baseline Grade 1 AST/ALT or total bilirubin who require dose delays for reasons other than a 2-grade shift in AST/ALT or total bilirubin may resume treatment in the presence of Grade 2 AST/ALT OR total bilirubin
- Subjects with combined Grade 2 AST/ALT AND total bilirubin values meeting discontinuation parameters should have treatment permanently discontinued

- Drug-related pulmonary toxicity, diarrhea, or colitis, must have resolved to baseline before treatment is resumed. *Subjects with persistent Grade 1 pneumonitis after completion of a steroid taper over at least 1 month may be eligible for retreatment.*
- Drug-related endocrinopathies adequately controlled with only physiologic hormone replacement may resume treatment.

If the criteria to resume treatment are met, the subject should restart treatment at the next scheduled timepoint per protocol. However, if the treatment is delayed past the next scheduled timepoint per protocol, the next scheduled timepoint will be delayed until dosing resumes.

If treatment is delayed or interrupted for > 6 weeks, the subject must be permanently discontinued from study therapy, except as specified in discontinuation section.

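### Table 1 releases a first ALT hold on THU-Dec only below 2.5 x ULN, so a liver-metastasis patient enrolled at 2.5 to 5 x ULN cannot restart on return to baseline after a drug-attributed rise below grade 3

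*Combined protocol and SAP*

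**What the plan says.** Section 4.1, criterion 7, gives two entry limits for AST and ALT: 2.5 x ULN in general, and 5 "X ULN for subjects with liver metastases".

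The ALT row of Table 1 in Section 7.1 has a single trigger for THU-Dec: "ALT ≥ 2.5X the upper limit of normal". The action depends on attribution. The investigator is first to look for another explanation of the worsening, and the instruction where none "are identified, hold THU-Dec until levels recover below threshold, then restart with decrease in dose by 1 capsule each of Dec and THU". For a recurrence, the same row lets dosing resume on recovery from, or resolution of, the toxicity, and gives no number.

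The paragraph after Table 1 covers non-hematologic toxicity of grade 3 or higher. Its release is different: "Hold drug until recovery to grade 1 or baseline", followed by a one-capsule reduction.

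Section 3.3 replaces a subject who takes fewer than 12 of the 16 doses intended in the first 8 weeks. This clause makes no exception for doses missed because of toxicity.

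**The concern.** For a patient who enters at or above 2.5 x ULN, the release level lies at or below the value that eligibility accepted. If ALT rises, the rise is attributed to THU-Dec, and ALT then returns fully to the entry value, the event has resolved but the row still forbids restart.

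The plan gives no reason for this, and it fits poorly with its surroundings. A grade 3 event may be released at baseline while a milder one may not. It also works against the row's own stated aim of keeping administration regular, at a lower dose if need be. At stake is exposure to the experimental component in patients the sponsor chose to admit, and avoidable replacements under Section 3.3.

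**Working it through.** The plan states no figure on this point, so the check compares the rules and then counts doses.

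**Inputs**
- Entry ALT, b, in multiples of ULN: up to 5 with liver metastases (4.1).
- First-hold release: ALT below 2.5 (Table 1).
- Grade 3 or higher release: grade 1 or baseline (7.1, after Table 1).
- THU-Dec twice weekly (6.2); at least 12 of 16 doses in 8 weeks (3.3).
- Chemistry on Day 1 and Day 15 of each 4-week cycle (10.0).

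**Release**
- If b < 2.5, return to b is below the threshold and the hold ends.
- If 2.5 ≤ b ≤ 5, return to b leaves ALT at or above 2.5 and the hold continues.
- Example: entry 3.0, attributed rise to 4.5, return to 3.0. Because 3.0 is not below 2.5, restart is not permitted.

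The fall below the entry value that restart requires is more than 1 − 2.5/b:
- b = 2.5: any value just below entry.
- b = 3: 1 − 2.5/3 = 16.7%.
- b = 4: 1 − 2.5/4 = 37.5%.
- b = 5: 1 − 2.5/5 = 50%. This is an arithmetic limit only. The documents do not print the ALT grade cut-offs. If grade 3 is assumed to start above 5 x ULN, any rise from 5 is already grade 3 and is released at baseline.

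**Comparison within Table 1.** The creatinine row sets its threshold from the pre-treatment value; one of its triggers is "Doubling of creatinine (if pre-treatment value 0.9-2.9 mg/dL". In each of its bands the threshold lies above the pre-treatment value, so return to baseline always ends the hold. The ALT row lacks that property for b ≥ 2.5.

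**Doses, illustrative case**
- Planned: 2 x 8 = 16. Misses allowed: 16 − 12 = 4 doses, or 2 weeks.
- Hold at Cycle 1 Day 15: weeks 1–2 taken, 2 x 2 = 4 doses. ALT is back at its entry value by Cycle 2 Day 1.
- With a baseline release, restart at Cycle 2 Day 1: 4 + (4 weeks x 2) = 12. Not replaced.
- As written, if ALT first falls below 2.5 at Cycle 2 Day 15: 4 + (2 weeks x 2) = 8. Replaced.
- As written, if it does not fall below 2.5 within 8 weeks: 4. Replaced.

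A reduced dose is counted as a dose taken. Unscheduled ALT checks could shorten a hold but would not change the release level.

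**The case against.** **Rarity and attribution.** The patient must be one of the 40 planned for the combination arm, have liver metastases, enter at 2.5 x ULN or above, and have a rise below grade 3 with no other cause found. Liver metastases are an obvious other cause, and the row says neither drug is expected to be hepatotoxic. This stands as a limit on size. It does not answer the point, because attribution decides whether a hold starts, not when it ends.

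**An absolute limit may be deliberate.** Wanting a lower ALT before re-exposure to a suspected drug is a defensible instinct. It is hard to reconcile with release at baseline for the more severe event.

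**Other rules might repair it.** The resume criteria in 7.3 release study drug at grade 1 or below "or baseline value, with the following exceptions". They belong to the nivolumab section and follow a sentence on nivolumab delay. Section 7.2 raises a dose or frequency; it does not restart a held drug.

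**The dose contrast is fine-edged.** Exactly 12 doses leaves no slack, and visits have a ±4-day window. One more missed dose leads to replacement under either wording. This stands, so the count is an illustration.

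**Stronger readings a reader might infer, which the documents do not support**
- *These patients are on hold from day one.* The figure is met at entry, but the row speaks of worsening without another cause, and 6.2 ties non-hematologic dose changes to toxicity attributed to study drug. An unchanged entry value would probably not be held.
- *Every ALT hold is locked.* Only the first is tied to the number; recurrent holds end on recovery.
- *Nivolumab resumes while THU-Dec stays off.* Section 7.3 does not require a nivolumab delay for grade 2 laboratory abnormalities, and its ALT-specific baseline terms cover only normal and grade 1 baselines. Nivolumab may never be held for this event, so that sequence is not established.

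**Conclusion.** The point holds in a narrow form. It concerns combination-arm patients with liver metastases, entry ALT of 2.5 to 5 x ULN, and a first drug-attributed rise below grade 3. For them, full return to baseline does not permit restart, and no other THU-Dec rule supplies a release. It is a worthwhile correction of modest weight.

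The number affected cannot be derived from the documents and is probably small. For one affected patient, the loss can be 4 or 8 of the first 16 doses against a baseline release, enough to cause replacement.

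A reader might infer that the efficacy analysis is altered. It is not: Section 12.1 defines the response rate over all randomized subjects, and Section 12.2 puts all randomized subjects in the primary efficacy dataset. No power or alpha figure changes.

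The verdict assumes that the paragraph after Table 1 governs ALT rises of grade 3 or higher, and that the resume criteria in 7.3 apply to nivolumab only. If the sponsor meant them to cover THU-Dec as well, two release rules conflict and the row still needs the correction.

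**What to change.** In the ALT row of Table 1, extend the first-hold release with the words *or to baseline if the pre-treatment ALT was 2.5 x ULN or higher*. Keep the one-capsule reduction and the clause on other causes. Leave the trigger to worsening with attribution, and leave the grade 3 or higher paragraph and the other rows unchanged.

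Do not replace the trigger with a multiple of baseline. A 1.5-fold rise would put it at 1.5 x 2.5 = 3.75 to 1.5 x 5 = 7.5 x ULN, above the 5 x ULN entry ceiling for any entry value over 5/1.5 = 3.33. It would also make the baseline release redundant, because the threshold would always exceed baseline.

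The cost is a wording amendment to one row. The screening chemistry panel already supplies the pre-treatment value, so no new test is needed. The small downside is that THU-Dec restarts, at a reduced dose, at an ALT level that eligibility already accepts.
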